## 2.5 Study Instruments

### 2.5.1 Screening Measures

#### *K-10*

Kessler-10 Psychological Distress Scale is a 10 item self-report questionnaire used for determining whether someone, and to what extent, experiences psychological distress (Kessler et al, 2002). The questions in the instrument are rated on 1 to 5 Likert type scale (from none of the time to all of the time), higher scores representing higher levels of stress the individual experienced in the last thirty days. There is no standard cut-off score; for this study we will use a score of >15 to align it with the previous similar research that was carried out with Syrian refugees (de Graaff et al, 2020). The K10 is available in Dari by the Transcultural Mental Health Centre (TMHC).

---

 Kessler Psychological Distress Scale in Dari language, <https://www.dhi.health.nsw.gov.au/transcultural-mental-health-centre-tmhc/resources/multilingual-resources-by-title/kessler-10>

## 2.5.2 Feasibility Measures

The primary outcome of this study is to assess the feasibility and acceptability of PM+ EP among young populations in Afghanistan. Feasibility will be evaluated based on participant retention rates, intervention and assessment completion rates, and the frequency of engagement with provided resources. Acceptability will be assessed through participant feedback and dropout rates. Additionally, qualitative data from process evaluation interviews will provide further insights into feasibility and acceptability by exploring participants' perceptions of the intervention and their willingness to engage in future studies.

## 2.5.3 Other Measures

### *HSCL-25*

Hopkins Symptom Checklist-25 (HSCL-25) is a 25 item self-report questionnaire assessing symptoms of psychological distress; 10 items for anxiety symptoms and 15 items for depression symptoms (2 of which identify somatic symptoms) (Mollica et al, 1987). The items are rated on a 4-point Likert scale, ranging from 1 (never) to 4 (always) with the anxiety scale ranging from 10-40 and the depression scale from 15-60. The total scale (range 25-100) represents psychological distress. It has been translated to several languages and validated among culturally diverse refugee adolescent population. Researchers who have gathered data from Afghan unaccompanied asylum seekers recommended a cut-off of 69.00 for total score, 20.00 for anxiety, and 33.21 for depression (Bronstein et al, 2013). The HSCL-25 is available in Dari, created by researchers Kenneth E Miller et al.

### *The Aggression Questionnaire (AGQ)*

The Aggression Questionnaire (AGQ) is a 29-item self-report questionnaire that measures both acts of aggression and traits that indicate a temperament to be aggressive or violent. The questionnaire covers four major components of aggression; physical aggression, verbal aggression, anger and hostility. Participants are asked to rate statements based on how characteristic they are of them. Answers are rated on a seven-point Likert scale ranging from 1 (Extremely uncharacteristic of me) to 7 (Extremely characteristic of me) with the total score ranging between 29 and 203. (Buss and Perry, 1992). The AGQ scale will be translated by PoMA's Afghan translator and checked for correct clinical terminology by a clinical team member.

### *The PTSD Checklist for DSM-5 (PCL-5)*

The PTSD Checklist for DSM-5 (PCL-5) is a 20 item self-report measure that measures symptoms of PTSD. All questions follow the same structure of "In the past month, how much were you bothered by...". Each question is scored from 0 (Not at all) to 4 (Extremely). Consistent with the DSM-5, the four symptom clusters are represented in the PCL-5 by the following subscales; Re-experiencing (Criterion B), Avoidance (Criterion C), Negative Alterations in Cognition and Mood (Criterion D), and Hyperarousal (Criterion E). Given the PCL-5 questions closely reassembled the diagnostic criteria in the DSM-5-TR, a provisional PTSD diagnosis can be made based on the following rule. The DSM-5 diagnostic criteria requires at least: 1 Criterion B item (questions 1-5), 1 Criterion C item (questions 6-7), 2 Criterion D items (questions 8-14), and 2 Criterion E items (questions 15-20). A score of 2 (Moderately on the likert scale) or higher is an endorsed symptom. Initial research suggests that a PCL-5 cutoff score between

---

 HSCL-25 scale in Dari, [\(PDF\) Hopkins Symptom Checklist 25-Dari](#)

31-33 is indicative of probable PTSD across samples (Weathers et al, 2013). The PTSD Checklist for DSM-5 (PCL-5) is available in Persian (Farsi), created by researchers Homeria Varmaghani et al.

#### **WHODAS 2.0**

WHO Disability Assessment Schedule (WHODAS 2.0) is an assessment tool developed by the World Health Organization (WHO) to measure health and disability for both research and clinical purposes (WHO, 2012). The instrument captures the functionality on six domains which are; 1) Cognition, 2) Mobility, 3) Self-care, 4) Getting along, 5) Life activities, and 6) Participation. The questions inquire about the experiences of difficulties in the specific domains of functionality within the last thirty days. Difficulties are scored on a five-point Likert scale ranging from 1 (none) to 5 (extreme), before summation (range 12-60). Higher scores indicate worse functional impairment. WHODAS 2.0 is available in Persian (Farsi), shared by the World Health Organization (WHO).

#### **2.5.6 Fidelity Assessment**

Protocol adherence will be evaluated through two methods. First, helpers will complete a session-by-session checklist after each session, indicating which core components of PM+ EP were delivered. Second, with informed consent, sessions will be audio-recorded, and approximately 10% of these recordings will be analyzed alongside the checklists to assess fidelity.

#### **2.5.7 Adverse Event Reporting**

Adverse events (AE) can be defined as any undesirable event that occurs to a participant or facilitator during the study. A serious adverse event (SAE) refers to any event that causes a serious medical emergency. Any AE or SAE will be reported promptly by the investigator to the ethics board (WCG Clinical). Any serious adverse events, such as incidents that are life threatening, require hospitalization for an ongoing duration, result in significant disability, or surgical intervention, may result in the study being temporarily paused while the situation is reviewed and necessary safety measures are addressed.

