
This pilot study will assess the feasibility, acceptability, and safety of implementing the culturally adapted PM+ EP among a novice population in Afghanistan. The study will examine the process of cultural adaptation and implementation, evaluating whether these interventions are practical and well-received by the target population. As a secondary objective, the study will explore the association

between mental health symptoms—such as depression, anxiety, aggression, and impaired functioning—and experiences of violence among young people in Afghanistan. Using our chosen instruments, we can examine key factors contributing to violence at baseline and explore how differences in mental health outcomes relate to behavioural change. Ultimately, the findings may inform the development of scalable mental health interventions that support improved mental health outcomes, daily functioning, and a reduction in violence.

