### **3. Analysis**

To evaluate the feasibility and acceptability of the intervention, qualitative analysis will be conducted through interviews with participants and facilitators, in addition, quantitative data will be gathered on mental health symptoms and behavioral outcomes. Qualitative data will be analyzed using ATLAS.ti to explore participant experiences and inform future intervention development. Interview transcripts will be imported into the software for systematic coding. An initial coding framework will be developed both deductively, based on study objectives, and inductively, based on emerging data. Two researchers will independently code a subset of transcripts, refining the codebook through consensus discussions to ensure consistency. All transcripts will then be fully coded, and thematic analysis will be conducted to identify key patterns and relationships. Findings will be used to complement

---

 DSM-5 (PCL-5) in Persian, [Psychometric Properties of the Persian Version of the Posttraumatic Stress Disorder Checklist for DSM-5 \(PCL-5\)](#)

 [WCG Clinical Services: Improving Clinical Trial Quality & Efficiency](#)

quantitative outcomes, providing a deeper understanding of feasibility, acceptability, and potential mechanisms of change within the intervention. To analyse quantitative data, mean differences in subscale scores and total scores between baseline (T1) and follow-up assessments (T2 and T3) will be determined. Linear mixed models will be employed to analyze feasibility and acceptability data, with treatment as a fixed effect, baseline endpoint measurements as covariates, and subjects as a random effect. This approach will allow for the assessment of trends in participant retention, session attendance, and intervention adherence over time while accounting for individual variability.

Feasibility will be assessed through intervention-specific metrics, including recruitment and consent rates, session attendance, assessment completion, protocol adherence, and occurrences of adverse events. Qualitative data collected through Process Evaluation interviews will complement these findings, providing contextual insights and a deeper understanding of the feasibility and acceptability of the program.

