#### 4. Ethics Approval

The study has received IRB ethics approval for this study from the Ministry of Public Health (MoPH) in Afghanistan and from WCG Clinical in the US (International approval). Both MoPH and WCG reviewed our study protocols, the Principal Investigator, and materials such as the data collection tools and consent forms, and provided approval to implement the pilot RCT, collect personal data from participants, and publish our findings.

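### The adverse-event count mixes facilitators with participants, and no adverse-event inquiry common to both arms is scheduled, which limits what the pilot can say about safety

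*Protocol*

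**What the plan says.** - **Aim.** Section 1 says that the pilot will "assess the feasibility, acceptability, and safety of implementing" the adapted programme. Section 2.3.3 adds the question of whether such interventions can be scaled safely.
- **Use of the count.** Section 3 lists the feasibility metrics, which it calls intervention-specific, and ends the list with "protocol adherence, and occurrences of adverse events". The same section plans linear mixed models for feasibility and acceptability data, with treatment as a fixed effect.
- **Definition.** Section 2.5.7 defines an adverse event as "any undesirable event that occurs to a participant or facilitator during the study".
- **Serious events.** Section 2.5.7 first says that a serious adverse event "refers to any event that causes a serious medical emergency". A later sentence, on pausing the study, gives as examples life-threatening incidents, prolonged hospitalisation, significant disability and surgery.
- **Contacts.** Section 2.3 gives PM+ EP participants six individual sessions within one calendar month. All participants complete four surveys at T1, T2 and T3. Neither the text nor Table 1 lists an adverse-event item at any of these points.
- **Facilitators.** Section 2.3.1 has them deliver the sessions and also carry out consent and screening.
- **Boards.** Section 2.5.7 names WCG Clinical as the recipient of reports. Section 4 states that the study has "IRB ethics approval for this study from the Ministry of Public Health (MoPH) in Afghanistan and from WCG Clinical in the US".

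**The concern.** A count that is to inform a safety aim needs a clear population and a known way of being collected. Here neither is settled.

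The definition takes in facilitators. After allocation their stated role is to deliver PM+ EP, so an event that befalls a facilitator during delivery has no counterpart in the waiting group. It also does not belong over a denominator of 30 participants per arm.

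The protocol does not say when, how or by whom participants are asked about events. A PM+ EP participant speaks with a facilitator six times in the first month. A waiting-group participant has only questionnaires that do not ask. If events come to light through contact, the PM+ EP arm can record more of them with no difference in true harm. A pilot meant to inform a larger trial could then report a misleading safety picture in either direction: an apparent excess under PM+ EP, or a real excess dismissed as a product of closer contact.

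The wording on serious events and on the receiving board leaves room for inconsistent classification and reporting.

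**Working it through.** The protocol states no adverse-event rate and no detection figure, so there is nothing of its own to reproduce. The check counts contacts and then asks how far unequal contact could distort the count.

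**Step 1. Scheduled contacts after baseline (section 2.3).**
- PM+ EP: 6 sessions + T2 + T3 = 8.
- Waiting group: T2 + T3 = 2.
- From T1 to T2 this is 7 against 1. From T2 to T3 it is 1 against 1.

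**Step 2. Assumptions (not in the protocol).**
- The true risk is the same in both arms.
- Each contact after an event reveals it with probability q, independently of the other contacts. With k contacts remaining, detection is 1 − (1 − q)^k.
- Events fall evenly over about four months: one month of sessions and three months to T3.
- The six sessions and T2 divide the first month into seven equal intervals. In PM+ EP an event in that month therefore has k = 8, 7, 6, 5, 4, 3 or 2 contacts left. In the waiting group k = 2.
- An event after T2 has one contact left, T3, in both arms.

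**Step 3. q = 0.2.**
- First month, PM+ EP: the mean of 0.832, 0.790, 0.738, 0.672, 0.590, 0.488 and 0.360 is 0.639.
- First month, waiting group: 1 − 0.8² = 0.36.
- Whole period, PM+ EP: 0.25 × 0.639 + 0.75 × 0.20 = 0.31.
- Whole period, waiting group: 0.25 × 0.36 + 0.75 × 0.20 = 0.24.
- Ratio: 0.31 / 0.24 = 1.3.

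**Step 4. q = 0.3.**
- First month, PM+ EP: the mean of 0.942, 0.918, 0.882, 0.832, 0.760, 0.657 and 0.510 is 0.786. Waiting group: 1 − 0.7² = 0.51.
- Whole period: 0.25 × 0.786 + 0.75 × 0.30 = 0.42 against 0.25 × 0.51 + 0.75 × 0.30 = 0.35.
- Ratio: 0.42 / 0.35 = 1.2.

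**Step 5. Upper extreme: every event occurs before the first session.** All 8 or 2 contacts can then reveal it, and the ratio is [1 − (1 − q)^8] / [1 − (1 − q)^2].

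| q | PM+ EP | Waiting group | Ratio |
|---|---|---|---|
| 0.1 | 0.57 | 0.19 | 3.0 |
| 0.2 | 0.83 | 0.36 | 2.3 |
| 0.3 | 0.94 | 0.51 | 1.8 |
| 0.5 | 1.00 | 0.75 | 1.3 |
| 0.9 | 1.00 | 0.99 | 1.0 |

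**Step 6. What the model leaves out.** It treats T2 and T3 as able to reveal events in both arms. The surveys list no adverse-event item, so the waiting group's true chance at those points could be lower. Against that, the protocol does not exclude unscheduled reports, which would narrow the gap.

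**Step 7. Texts side by side.** Significant disability, one of the examples in section 2.5.7, need not involve a medical emergency, so the two descriptions of a serious event do not cover the same set. Section 2.5.7 names one receiving board where section 4 names two approving boards.

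**The case against.** The strongest reply is that no between-arm comparison of adverse events is planned. Section 3 calls the metrics intervention-specific and groups adverse events with attendance and adherence, which have no control counterpart. The sentence explaining the mixed model mentions retention, attendance and adherence, not adverse events. Describing events under PM+ EP is ordinary for a pilot of 60 without a power calculation. This stands. A reader might infer that a planned safety comparison is invalid, or that the question of safe scaling cannot be answered at all. The protocol supports neither. What remains is that the treatment term and the randomised waiting group invite a comparative reading, and that even a descriptive count is blurred by staff events.

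Second, the broad definition may serve only reporting to the ethics board, where each report would show whom it concerns, and the protocol nowhere says that the events will be pooled in an analysis. That is fair, but section 3 uses the same undivided term for its metric. It would also be wrong to say that facilitators meet only PM+ EP participants, since they carry out consent and screening as well.

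Third, the count of 8 against 2 is an inference from the schedule. No section makes sessions or surveys the route of detection, and q has no source. This also stands. The ratios of 1.8 to 2.3 at q = 0.2 to 0.3 require every event to precede the first session, so they are an extreme and not an estimate.

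Fourth, the later sentence on serious events gives examples within a rule on pausing and may not be meant as a definition. That makes it loose drafting and not a flat contradiction.

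Finally, a reader might infer that the Ministry of Public Health would not be told of events. The protocol does not say so; it only fails to name that board.

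**Conclusion.** The point holds as a limit on interpretation, and it is minor. Followed as written, the plan gives an adverse-event count that can mix staff with participants and has no like-for-like figure from the waiting group. Under equal true risk the apparent ratio is about 1.2 to 1.3, given events spread evenly over about four months, evenly spaced sessions and a detection probability of 0.2 to 0.3 per contact. It rises to 1.8 to 2.3 at the same probabilities if all events come before the first session, and it approaches 1 as detection becomes complete. All of these inputs except the contact schedule are assumptions, so the actual size is unknown. No planned test is affected. The wording on serious events and on the receiving board needs reconciling but does not bear on the size.

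**What to change.** 1. Put one identical adverse-event question to all participants at T2 and T3, and add it to Table 1.
2. Base any comparison between arms on those answers alone. Contacts are then 2 against 2.
3. Tabulate events reported in sessions separately, as a description of PM+ EP.
4. Tabulate facilitator events separately from participant events. The broad definition can stay for reporting purposes.
5. Reconcile the two descriptions of a serious event in section 2.5.7.
6. Reconcile sections 2.5.7 and 4 by stating which approving board or boards receive reports.

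The cost is one added item in two existing surveys, its translation, and a few words of protocol text. Restricting the comparison to T2 and T3 gives up some sensitivity, because events forgotten by then are missed, but the questioning is the same in both arms.

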### 2.2 Participants

Participants for this study will be recruited through health-related entry pathways, such as health clinics, gender-focused support services, community hubs, and ministries and stakeholders working within the mental health sector in Afghanistan. Participants will be men and women between the ages of 16 and 30 residing in Afghanistan, who experience psychological distress. Eligible participants will have elevated levels of psychological distress measured by the Kessler-10 Psychological Distress Scale (K10 > 15) (Andrews, 2001). They should also meet the inclusion criteria of having the ability to read and write in Dari. Those who present as an imminent suicide risk, with psychosis, or those with neurological or cognitive disabilities, will be excluded. Potential participants will be asked to provide their contact information and will be invited to complete the K10 self-report assessment, to measure their level of psychological distress. Once determined as having elevated levels of psychological distress, 60 eligible participants will be invited to partake in the study. Participants will be assigned a case number, to protect their identity and provide anonymity. Participants will be asked to provide written consent in Dutch/English and/or Dari and be made aware that they are permitted to withdraw from the study at any point.

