### 2.3 Procedure

Participants receiving PM+ EP will meet their facilitator individually, someone of the same gender, and receive the intervention through sessions conducted over Zoom or a similar platform; mitigating the difficulties around accessing psychological support, and the risks associated with safety of participants and stigma around mental health. Participants will receive six individual sessions of PM+ EP over the period of one calendar month.

All participants will complete four surveys for assessment at study points T1, T2 and T3; The Hopkins Symptom Checklist 25 (HSCL-25) to measure for anxiety and depression (Mollica et al, 1987), The Aggression Questionnaire (AQG) to measure violent behaviours (Buss and Perry, 1992), The Post Traumatic Stress Disorder (PTSD) Checklist for DSM-5 (PCL-5) will screen participants for symptoms of PTSD (Weathers et al, 2013), and cognitive ability and overall ability to function will be measured by WHO Disability Assessment Schedule 2.0 (WHODAS 2.0) (WHO, 2012). The latter has been used in studies looking at PTSD and other trauma-symptoms in low-resource settings, to assess the communities' impaired daily functioning (Hamdani et al., 2020). After the final assessment has been complete, a non-random sample of participants will be invited to partake in an interview – the Process Evaluation -, to gather qualitative data to assess the feasibility and acceptability of the program.

The timeline and frequency at which the instruments that will be used for screening, baseline and post intervention are listed in the table below. Some of the listed instruments have translations in Dari or Farsi (Afghan Persian/Iranian Persian). In case there is no translation, the instrument will be translated and back translated by the research team.

*Table 1. Measure Overview and Timeline*

Assessment Timeline					
Enrolment T0	Allocation	Baseline T1	Post-intervention T2	Follow-up - 3 months Post- intervention T3	Close-out
Enrolment:					
Eligibility criteria	X				
Informed consent	X				
Allocation		X			
Intervention:					
PM+ EP		X	X	X	X
Waiting Group					
Assessment:					
K10	X				
HSCL-25		X	X	X	
AGQ		X	X	X	
DSM-5 (PCL-5)		X	X	X	
WHODAS 2.0		X	X	X	
Process Evaluation					X

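### The SAE definition is medical only, so new psychosis without admission and detention or reprisal after disclosure are not classed as serious and have no explicit route to pause review

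*Protocol*

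**What the plan says.** Section 2.5.7 (Adverse Event Reporting) has four elements that matter here.

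- The AE definition is broad: "Adverse events (AE) can be defined as any undesirable event that occurs to a participant or facilitator during the study".
- The SAE definition is narrow: "A serious adverse event (SAE) refers to any event that causes a serious medical emergency".
- Reporting does not depend on seriousness: "Any AE or SAE will be reported promptly by the investigator to the ethics board".
- The pause provision is written for serious adverse events only, "such as incidents that are life threatening, require hospitalization for an ongoing duration, result in significant disability, or surgical intervention, may result in" a temporary halt while the matter is reviewed. It is permissive, not mandatory.

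Two other sections show which non-medical harms the protocol already has in view. Section 2.2 (Participants) says: "Those who present as an imminent suicide risk, with psychosis, or those with neurological or cognitive disabilities, will be excluded". Section 2.3 (Procedure) explains that sessions are held by video partly to reduce "the risks associated with safety of participants and stigma around mental health".

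Safety is also among the stated aims. The end of Section 1 names it beside feasibility and acceptability, Section 2.3.3 asks whether the intervention could be scaled safely, and Section 3 lists adverse event occurrences among the feasibility metrics.

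**The concern.** The general SAE sentence and every example attached to it describe a bodily or medical event. None is psychiatric and none concerns personal security. Yet the harms most specific to this trial are of those two kinds. Participants are selected for distress. The Emotional Processing module (Section 2.4) asks them to revisit adverse memories. Section 2.3 treats exposure and stigma as real risks in this setting. Two of the psychiatric states in question are grave enough to bar entry, but nothing says how they are classed if they arise after enrolment.

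Because any undesirable event is reportable, the SAE label is the only severity distinction in the safety section and the only status linked to a pause. If a foreseeable grave harm does not carry that label, the safety summary will show it among ordinary adverse events, and the protocol gives no explicit prompt to consider stopping to review it. For a pilot meant to inform scaling, that is a weakness in the safety record.

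**Working it through.** No arithmetic applies, and the protocol states no figure to reproduce. The check is to take each kind of event and test it against the wording of Section 2.5.7.

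| Event in a participant after enrolment | AE, and so reported? | Meets the general SAE sentence? | Meets a listed example? |
|---|---|---|---|
| Suicide attempt | Yes | Ordinarily yes | Ordinarily yes, as life threatening |
| Prolonged psychiatric admission | Yes | Depends on the case | Yes, as hospitalization |
| New imminent suicide risk, no attempt | Yes | Not settled | Only if read as life threatening |
| New psychosis, no admission | Yes | Only if the episode is separately judged a medical emergency | No, unless it also threatens life or disables |
| Detention, reprisal or expulsion from home after disclosure, no serious injury | Yes | No | No |

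Four steps follow from this.

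1. **Reporting.** Every row is an undesirable event that befalls a participant, so every row is an AE. AEs and SAEs go to the ethics board alike, so no row escapes reporting.
2. **Counting.** The feasibility metric in Section 3 is the occurrence of adverse events, not of serious ones. Every row is counted there whatever its SAE status.
3. **Seriousness.** The last two rows are not SAEs by their nature. They become serious only through some further medical consequence. The third row turns on one reader's interpretation of a threat to life.
4. **Pause review.** The provision names SAEs only. The last two rows therefore have no explicit route to it, and the third has one only on a generous reading. The text does not forbid a review prompted by an AE; it simply does not provide for one.

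Set beside Sections 2.2 and 2.3, the result is uneven: psychosis is serious enough to exclude a candidate, but its onset in an enrolled participant is not, as such, a serious event.

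**The case against.** The strongest reply is that little depends on the label. Reporting is complete, the adverse event count is unchanged, the pause is discretionary even for a clear SAE, and no estimate in the trial is affected. The examples are introduced as illustrations, so an investigator may treat other events as serious, and most would regard imminent suicide risk as life threatening. All of this stands, and it is why the point is minor. It does not answer the two clearest cases. Illustrative examples can only illustrate the class that the general sentence sets, and that class is medical emergencies. Detention without injury is outside it on any reading, and psychosis managed at home is outside it unless the episode happens to become an emergency.

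A reader might infer three stronger points. The document does not support them.

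- **That the section holds two conflicting SAE definitions, and that handling depends on which one is applied.** The list illustrates the general sentence and is not a rival to it. It is true that disability or surgery need not be an emergency, but the list names those events, so they are covered. The harms at issue are missed because both wordings are medical, not because the wordings differ.
- **That these harms go unreported or distort the feasibility result.** They do not, as the check shows.
- **That violence by a participant against an outsider must be recorded as an AE.** The AE wording does not reach it, but the protocol nowhere undertakes to record harm to outsiders. Aggression is an outcome, measured in both arms at T1, T2 and T3 with the Aggression Questionnaire. Recording such incidents would create sensitive records about participants. It would also pick up more of them in the arm that meets a facilitator for six sessions. That is a debatable design choice, not a defect.

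**Conclusion.** The point holds in a limited form. The SAE definition in Section 2.5.7 is confined to medical emergencies with medical examples. New psychosis without admission, and detention or reprisal after disclosure, are therefore not serious events under it. New imminent suicide risk is serious only on one reading.

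The loss is the classification as serious and the explicit link to pause review. Ethics-board reporting and the adverse event count are intact. The size cannot be put in numbers, because the protocol gives no rates for these events and none can be derived from it.

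The conclusion rests on two assumptions: that the wording is applied as written, and that a psychosis or reprisal case has no separate medical consequence that would make it serious in any event. Severity is low. The change is still worth making, because it is cheap and concerns harms that the protocol itself anticipates.

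**What to change.** Replace the general SAE sentence and the example list in Section 2.5.7 with one definition that serves both reporting and pause review. An SAE is any of the following:

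- death;
- a life-threatening event or other serious medical emergency;
- hospitalization, at the duration threshold now stated;
- significant disability;
- surgical intervention;
- a suicide attempt or new imminent suicide risk;
- new onset of psychosis;
- detention, physical assault or expulsion from home that results from disclosure of participation.

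Leave the AE definition and the reporting rule as they are, and keep the pause discretionary. Naming the disclosure-related harms avoids a further undefined use of the word serious.

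The cost is one paragraph of protocol text, with no new instrument, visit or analysis. The downside is a somewhat higher SAE tally, which the report should explain by reference to the wider definition.
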